8.8.2.7 TIME TO TMA RESPONSE

Time to TMA response (weeks) will be defined as the date of first exposure to the study drug to first occurrence of TMA response (derived as in Appendix II [Section 13.2]). Time to TMA response (weeks) will be evaluated for:

- Patients achieving TMA response (without a preceding ICE) at any time during the study. Note the
 patient in this case will be considered as a responder even if not any longer in TMA response at week
 24 or not (sustained response not required)
- Patients achieving TMA response at Week 24 without meeting an ICE (response must be sustained until Week 24)

The time to TMA response (weeks) will be analyzed in the same way as Time to Clinical Response (see Section §8.8.2.6 for details).

8.8.2.8 DURATION OF CLINICAL RESPONSE

Duration of clinical response (weeks) is defined as the time from the first observed clinical response until the response criteria is no longer fulfilled or until end of study. Duration of response will be defined for patients with clinical response without meeting an ICE. Mean and median duration of response, together with their 95% CI will be estimated using Kaplan-Meier method. Kaplan-Meier curves will also be presented. The start date will be defined as the date of the earliest clinical response. Loss of clinical response as per appendix I (Section 13.1) reported TA-TMA relapse (from Survival Status eCRF form), and death from any cause will be

Page 27 of 39

considered events, with the date of loss of clinical response, date of first reported TA-TMA relapse or date of death, whichever occurs first, defining the event date. Patients without events (i.e., still in clinical response) up to Week 24 will be censored at the date of the last clinical response evaluation prior to end of study.

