4. STUDY DESCRIPTION

4.1 STUDY DESIGN

This is a prospective, open-label, multicenter, single-arm, pilot study to evaluate the PK, PD, efficacy, and safety of pegcetacoplan in patients with TA-TMA after HSCT.

The study will enroll 12 patients with TA-TMA, who will receive treatment with open-label pegcetacoplan at the planned dose regimen presented in Section §4.2.

The planned study duration for each patient is up to 24 weeks. The study will consist of the following periods:

- Screening period (up to 2 weeks),
- Treatment period (up to 16 weeks) and
- Follow-up period (up to 12 weeks).

The main analysis will be performed after all enrolled patients have completed the follow-up period and performed the End of study visit at the Week 24 visit or the Early Termination visit in case of early discontinuation.

A Safety Review Committee (SRC) will assess the progress and cumulative PK, PD, safety and efficacy data of the study.

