5. SAMPLE SIZE AND POWER CALCULATION

This is a pilot study, and the sample size is based on practical rather than statistical aspects.

A total of 12 patients will be included and treated in the study. With 12 patients included, it is estimated that 9 patients will complete at least 4 weeks of treatment, which is deemed sufficient to characterize the PK of pegcetacoplan in patients with TA-TMA to an appropriate precision. In addition, 12 patients will provide a 72% probability to observe a response rate of at least 8 responders of the 12 patients recruited (assuming the true response rate is 70%).

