8.8.2.9 DURATION OF TMA RESPONSE

Duration of TMA response (weeks) is defined as the time from the first observed TMA response until the response criteria is no longer fulfilled or until end of study. Duration of response will be defined for patients with TMA response without meeting ICE. The start date will be defined as the date of the earliest TMA response. Loss of TMA response as per appendix II (Section 13.2), reported TA-TMA relapse (from Survival Status eCRF form), and death from any cause will be considered events, with date of loss of TMA response, date of first reported TA-TMA relapse or date of death, whichever occurs first, defining the event date. Patients without events (i.e., still in TMA response) up to Week 24 will be censored at the date of the last TMA response prior to end of study.

The duration of TMA response (weeks) will be analyzed in the same way as Duration of Clinical Response (see Section §8.8.2.8 for details).

8.8.2.10 Proportion of Patients with TA-TMA relapse at week 24

Proportion of patients with TA-TMA relapse at week 24 will only be defined for patients reaching clinical response at some point of the study. TA-TMA relapse will be defined as reappearance of clinical/laboratory markers of TA-TMA as outlined in Inclusion Criterion #3. Counts and proportions of patients with and without relapse at Week 24 will be summarized. 95% Clopper-Pearson CI for proportion of patients with TA-TMA relapse will also be presented.

8.8.2.11 CLINICAL RESPONSE AT WEEK 12

Analysis of Clinical Response at Week 12 is covered in the Section §8.8.2.2.

8.8.2.12 TA-TMA RESPONSE AT WEEK 12

Analysis of TA-TMA Response at Week 12 is covered in the Section §8.8.2.3.

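### The Kaplan-Meier mean duration of response has no stated restriction time, so when the longest duration is censored it depends on an unstated, data-driven limit

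*SAP*

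**What the plan says.** SAP 8.8.2.8 plans the following for duration of clinical response: "Mean and median duration of response, together with their 95% CI will be estimated using Kaplan-Meier method". The clock starts at first response: "The start date will be defined as the date of the earliest clinical response". Events are loss of the response criteria, reported TA-TMA relapse and death from any cause. All other responders are censored: "Patients without events (i.e., still in clinical response) up to Week 24 will be censored at the date of the last clinical response evaluation".

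SAP 8.8.2.9 has a parallel rule, "Patients without events (i.e., still in TMA response) up to Week 24 will be censored at the date of the last TMA response", and takes over the method: "The duration of TMA response (weeks) will be analyzed in the same way as Duration of Clinical Response".

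Neither section gives a restriction time for the mean, a convention for a censored longest duration, or a rule for the case without events. SAP 8.1 and 11 name SAS 9.4 or later but no procedure or option. Protocol 8.3.4.2 asks only for Kaplan-Meier methodology and curves, so the mean is an addition in the SAP.

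**The concern.** A Kaplan-Meier mean is the area under the estimated curve. It estimates mean duration only if the curve falls to zero, which requires the longest observed duration to be an event. Here follow-up ends for everyone at Week 24, and continuing responders are censored there. If one of them has the longest duration, the curve stops above zero and the area has to be cut somewhere. Cutting at the last event and cutting at the last observation give different numbers, and the SAP does not choose between them.

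Duration of clinical response and duration of TMA response are both named secondary endpoints. With about 8 responders expected, a single early loss can determine the reported mean under one of these conventions. A reader of the results would see a figure labelled mean duration with a 95% CI and could not tell what it measures.

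**Working it through.** **Inputs from the documents.** Number of patients: "The study will enroll 12 patients with TA-TMA" (SAP 4.1). Follow-up: "The planned study duration for each patient is up to 24 weeks" (SAP 4.1). Assumed response rate: 70% (SAP 5). Post-baseline response evaluations at Weeks 1, 2, 3, 4, 6, 8, 10, 12, 14, 16, 20 and 24 (protocol Table 1).

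**The plan's own figure.** SAP 5 states that "12 patients will provide a 72% probability to observe a response rate of at least 8 responders of the 12 patients". With X ~ Binomial(12, 0.70), P(X ≥ 8) = 0.7237, so the 72% reproduces. The expected number of responders is 12 × 0.70 = 8.4, and 8 is used below.

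**Example A: two losses.** Eight responders, losses at 4 and 6 weeks, six censored at 20 weeks. The curve is 1 up to 4 weeks, 7/8 = 0.875 from 4 to 6 weeks, and 0.875 × 6/7 = 0.75 from 6 to 20 weeks.
- Area to the last event: 4 × 1 + 2 × 0.875 = 5.75 weeks.
- Area to the last observation: 5.75 + 14 × 0.75 = 16.25 weeks.

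**Example B: one loss.** Eight responders, first response at Weeks 1, 2, 2, 3, 4, 4, 6 and 8. The last of these is lost after 2 weeks. The other seven are censored at Week 24, with durations of 18 to 23 weeks.
- Area to the last event: 2 × 1 = 2.0 weeks.
- Area to the last observation: 2 + 21 × 0.875 = 20.4 weeks.

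B has fewer losses than A, yet its to-last-event mean is shorter (2.0 against 5.75 weeks). The to-last-observation means are in the expected order (20.4 against 16.25), but they run to different limits, 23 and 20 weeks. With no loss at all, the to-last-event mean cannot be computed.

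**How often the longest duration is censored.** The documents give no rate of loss of response, so it was assumed and varied. Simulation: 8 responders, first response at Weeks 2 to 12, exponential time to loss, loss dated at the next scheduled visit, censoring at Week 24, 4000 trials per scenario. A longest duration shared by an event and a censored patient counts as censored, because the curve then stays above zero.

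| Assumed loss by 20 weeks | Trials with longest duration censored |
|---|---|
| 10% to 50% | about 99% to 88% |
| 70% | 78% |
| 90% | about 51% |

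**What each convention reports at 10% to 50% loss.** The true mean restricted to 20 weeks falls from 19.0 to 14.4 weeks over this range.
- To the last event: there is no event in 48% of trials at 10% loss and 1% at 50% loss. Where it can be computed, the average stays between 11.3 and 12.2 weeks, so it hardly reflects durability.
- To the last observation: the average falls from 20.5 to 15.7 weeks. It follows durability, with a horizon that varies from trial to trial.

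**A fixed horizon.** Restricted to 12 weeks, example A gives 4 + 2 × 0.875 + 6 × 0.75 = 10.25 weeks and example B gives 2 + 10 × 0.875 = 10.75 weeks. They are in the right order and on one scale. In the simulation, the 12-week restricted mean averages 11.7 to 10.2 weeks against a true 11.6 to 9.8.

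**The case against.** The strongest case against runs as follows.

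- **Convention.** The documents do not say that the area will be cut at the last event. A reader might infer that the reported mean will be biased low, undefined, or unable to separate durable from short response. Those statements hold only for the to-last-event version, and the bias is not general even there: at 70% and 90% loss that version averages 11.0 and 8.2 weeks against true 20-week restricted means of 11.6 and 7.8. The to-last-observation version is always defined and follows durability. This objection stands. What remains is that the SAP does not say which version will be reported.
- **Frequency.** A reader might infer that the longest duration is almost always censored. The documents leave room for high loss: death counts as an event, protocol 4.1 cites mortality of up to 60% to 75%, and treatment ends at Week 12 or 16. If the censoring rule means the last evaluation before the Week 24 visit, that is Week 20, the shares at 70% and 90% loss fall to 51% and 33%. So censoring of the longest duration is likely unless most responders lose response, but not certain.
- **Consequence.** The analysis is descriptive. The same section gives the median and the curve, and the SAP also reports response at each visit, sustained response to Week 24 and the relapse proportion. A median reported as not reached is accurate. This stands and limits the severity.

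One possible defence fails. The definition in 8.8.2.8 lets duration run to the end of study, which might suggest that durations ending at Week 24 are complete. The same section treats those patients as censored.

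**Conclusion.** The concern holds as a minor point. When the longest duration is censored, the planned mean for clinical and TMA response is a mean restricted to a data-dependent time that the SAP does not state. The two possible cut-offs can differ by a wide margin: 5.75 against 16.25 weeks in example A, and 2.0 against 20.4 in example B. How often this arises rests on assumed loss rates, 8 responders, exponential loss and first response by Week 12. The dependence on the cut-off itself follows from the SAP's censoring rule and needs none of these assumptions. The documents do not support a claim that the mean will be biased low in general or that the endpoint as a whole is uninformative.

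**What to change.** In SAP 8.8.2.8 and 8.8.2.9, do one of two things:
- drop the mean; or
- replace it with a restricted mean duration to one prespecified horizon, with its 95% CI.

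Twelve weeks after first response is a possible horizon, with two conditions to write down. Patients who first respond after Week 12 are censored before reaching it, because follow-up ends at Week 24. Such patients are foreseen, since treatment may continue to Week 16 and response is evaluated at Weeks 14, 16 and 20. The horizon must also not exceed the longest observed follow-up.

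Keep the median, reported as not reached where that applies, and keep the curve. Add Kaplan-Meier proportions still in response at fixed times such as 4, 8 and 12 weeks.

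The cost is a sentence or two in each section and one setting in the analysis program. No protocol change is needed, because the protocol does not ask for a mean. The small downside is that the horizon has to be chosen in advance.

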8.8.2.9 DURATION OF TMA RESPONSE

Duration of TMA response (weeks) is defined as the time from the first observed TMA response until the response criteria is no longer fulfilled or until end of study. Duration of response will be defined for patients with TMA response without meeting ICE. The start date will be defined as the date of the earliest TMA response. Loss of TMA response as per appendix II (Section 13.2), reported TA-TMA relapse (from Survival Status eCRF form), and death from any cause will be considered events, with date of loss of TMA response, date of first reported TA-TMA relapse or date of death, whichever occurs first, defining the event date. Patients without events (i.e., still in TMA response) up to Week 24 will be censored at the date of the last TMA response prior to end of study.

The duration of TMA response (weeks) will be analyzed in the same way as Duration of Clinical Response (see Section §8.8.2.8 for details).

8.8.2.10 Proportion of Patients with TA-TMA relapse at week 24

Proportion of patients with TA-TMA relapse at week 24 will only be defined for patients reaching clinical response at some point of the study. TA-TMA relapse will be defined as reappearance of clinical/laboratory markers of TA-TMA as outlined in Inclusion Criterion #3. Counts and proportions of patients with and without relapse at Week 24 will be summarized. 95% Clopper-Pearson CI for proportion of patients with TA-TMA relapse will also be presented.

8.8.2.11 CLINICAL RESPONSE AT WEEK 12

Analysis of Clinical Response at Week 12 is covered in the Section §8.8.2.2.

8.8.2.12 TA-TMA RESPONSE AT WEEK 12

Analysis of TA-TMA Response at Week 12 is covered in the Section §8.8.2.3.

8.9 SAFETY ENDPOINTS AND ANALYSES

Safety analyses will be performed using the Safety set. All data relating to safety will be listed and summarized using descriptive statistics. No inferential statistical tests will be performed.

8.9.1 ADVERSE EVENTS

All AEs will be coded using MedDRA version current at the time of the DBL.

Pre-treatment AEs are those occurring between the ICF signature and the first IMP administration. TEAEs are defined as those AEs that start or worsen after the first dose of IMP and up to 8 weeks after the last IMP dose. Events will be flagged as treatment-emergent unless sufficient data are available to conclude that the start/worsening occurred before the treatment was started.

If the severity or relationship is missing for one of the treatment-emergent occurrences of an adverse event for a patient, the maximal severity or relationship on the remaining occurrences will be considered. If the severity is missing for all the occurrences, a "missing" category will be added in the summary table.

An overall summary table of the number and percentages of patients within the following categories will be provided:

- Any TEAE,
- Any related TEAE,
- Any serious TEAE,
- Any related serious TEAE,
- Any non-serious TEAE,
- Any related non-serious TEAE,
- Any TEAE leading to withdrawal of pegcetacoplan,
- Any serious TEAE leading to withdrawal of pegcetacoplan,
- Any TEAE leading to drug interruption,
- Any TEAE that is considered as a Target Medical Event as defined in Table 2 Definition of Target Medical Events,
- Any TEAE leading to death.
- Any TEAE that were infusion site reactions (as per eCRF, both injection and infusion site reactions

will be included).

- Any device related TEAEs (as per eCRF),
- Any TEAE by severity (mild, moderate and severe).

Pre-treatment AEs will be listed.

TEAEs, serious TEAEs, non-serious TEAEs, TEAEs by severity (mild, moderate, and severe), TEAEs related to pegcetacoplan, TEAEs leading to the withdrawal of pegcetacoplan, TEAEs leading to drug interruption, TEAEs that are considered as Target Medical Events, TEAEs that were infusion site reactions, device related TEAEs and AEs leading to death will be summarized by SOC and PT. Three categories of selected target TEAEs (Target Medical Events, defined in Table 2 - Definition of Target Medical Events) that are considered as Target medical Events will be summarized a posteriori. Summaries will include incidence of AEs, and number of events. The severity of AEs and the relationship to the IMP will be summarized for each SOC and PT.

Pre-treatment AEs, TEAEs, serious TEAEs, non-serious TEAEs, TEAEs by severity (mild, moderate and severe), TEAEs related to pegcetacoplan, serious TEAEs related to pegcetacoplan, TEAEs leading to withdrawal of pegcetacoplan, and target medical events will be summarized by PT.

At each level of summarization, a patient is counted once if he/she reported 1 or more events at that level. These summaries by SOC and PT will be sorted by decreasing order of overall incidence of SOC and decreasing order of overall incidence of PT within SOCs. In case of identical frequencies, SOC and PT will be sorted alphabetically. The summaries by PT will be sorted by decreasing frequency of overall incidence of PT.

All AE data will be listed including onset date, duration, relationship to IMP, severity, seriousness, action taken with IMP, treatment of event and outcome.

8.9.2 HEMATOLOGY, SERUM CHEMISTRY AND COAGULATION

Summary statistics of quantitative laboratory results and changes from baseline will be summarized by visit. Shift tables of worst post-baseline assessments (including unscheduled observations) vs. baseline will be presented. For parameters with NCI-CTCAE toxicity grades for changes in both directions, the shift tables will be done using NCI-CTC toxicity grades, with separate parameters depending on the direction. For parameters with NCI-CTCAE toxicity grades for changes in only one direction, the shift tables will be done using the NCI-CTC toxicity grades and the normal ranges (Low, Normal, High, Missing). For parameters without NCI-CTCAE toxicity grades for changes, the shift tables will be done using the normal ranges. Out-of-range values will be flagged in data listings. In addition, scatterplots for lab parameters (baseline vs. post-baseline values) will be prepared.

8.9.3 URINALYSIS

Continuous results will be summarized together with changes from baseline similarly to hematology per visit, and categorical results will be summarized in frequency tables by visit. Tests for which normal ranges are provided will also be summarized by means of frequency and shift tables in the same way as the hematology results.

8.9.4 VITAL SIGNS, PHYSICAL EXAMINATION AND ECG

Summary statistics of vital signs (systolic and diastolic blood pressure, heart rate, respiration rate, and body temperature) and their changes from baseline will be presented by visit and timepoint.

Physical examination data will be presented in a listing.

The incidence of clinically significant abnormal ECG findings will be summarized by visit and timepoint.

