#### 6.5.5.6 Electrocardiograms

Single 12-lead ECGs will be recorded prior to dosing at the time points outlined in the schedule of assessments (Table 1). The ECG will be taken after the patient has been resting in the supine position for 5 minutes in a quiet environment and prior to any blood sampling procedures, unless specified at time points after timed blood sampling procedures.

The ECGs will be classified as normal, having a not clinically significant abnormality or having a clinically significant abnormality. For patients with an abnormal ECG, it is recommended that the ECG recording is reviewed by a cardiologist in addition to the treating investigator.

Any significant ECG finding present prior to the start of IMP administration is to be documented in the medical history section of the eCRF. Any significant ECG finding with an onset time after IMP initiation and that was not present at screening, or worsened during the study, is to be reported as an AE.

Clinically significant abnormal ECG findings should be reported as AEs (see Section 6.5.5.1.1 for details).

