6. ANALYSIS ENDPOINTS

6.1 PRIMARY ENDPOINTS

The primary PK endpoints of this study are PK parameters for pegcetacoplan on Day 1, 3, and 5: Area under the concentration-time curve over the dosing interval on days 1 to 3 ($AUC_{0-taud1-d3}$), 3 to 5 ($AUC_{0-taud3-d5}$) and 5 to 8 ($AUC_{0-taud5-d8}$). Maximum observed serum concentration (C_{max}), Time to the maximum observed serum concentration (T_{max}) and Observed serum trough concentration pre-dose (T_{tough}) at all visits.

The primary safety endpoints are as follows:

- Occurrence of treatment-emergent adverse events (TEAEs)
- Changes from baseline in laboratory parameters and vital signs
- · Occurrence of clinically significant abnormal electrocardiogram (ECG) findings
- Presence of antibodies to polyethylene glycol (PEG) and pegcetacoplan throughout treatment and follow-up periods

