8. ANALYTICAL PLAN AND STATISTICAL METHODS

8.1 GENERAL CONVENTIONS AND STATISTICAL CONSIDERATIONS

All statistical analyses will be performed, and outputs (TFLs) will be created using the SAS system version 9.4 or higher.

Data collected in this study will be presented in patient data listings and summary tables.

Descriptive statistics (number of patients with non-missing values, arithmetic mean, standard deviation (SD), median, first quartile [Q1], third quartile [Q3], minimum, and maximum) will be presented for continuous variables. For all PK parameters, the coefficient of variation (CV), geometric mean, and corresponding 95% confidence interval (CI) and geometric CV will be added to the summaries. All raw data will be presented to the original number of decimal places. Means and medians will be presented to 1 more decimal place than in the raw data. Standard deviations will be presented to 2 more decimal places than in the raw data.

• Geometric mean is calculated as follows:

$$\mu_g = \exp\left(\frac{\sum_{i=1}^n \ln x_i}{n}\right)$$

Where x_i is the value of interest for each patient.

• CV is calculated using SD and mean using the following formula:

$$CV (\%) = \frac{SD}{Mean} x 100$$

Geometric CV is calculated as follows:

$$GCV (\%) = \sqrt{\exp(SD^2) - 1} x 100$$

Where SD is the standard deviation of the log-transformed value of interest for each patient.

Frequency distributions (counts and percentages) will be presented for categorical variables. Percentages will be suppressed when the count is zero, however the category will still be displayed. If not specified otherwise, the number of observations with non-missing values will be the denominator for percentage calculation. Percentages will be presented to 1 decimal place. Further details on the handling of missing observations are given in Section §8.4.

Safety laboratory results reported as below or above limits of quantification, e.g., "<x.x", "<=x.x", ">x.x" or ">=x.x", will be summarized in the tables using the reported limit of quantification (LOQ). The listings will show the result as reported.

Calculations using dates (e.g., relative day after the first dose of the study drug) will adhere to the following conventions:

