8.3 STUDY VISITS AND ANALYSIS WINDOWS

Data will be summarized and analyzed based on the list of visits specified in Table 1 – Study Visits and Analysis Windows.

Table 1 – Study Visits and Analysis Windows

Period	Visit	Target Study Day	Analysis Window (study day)	Interval (days)
Screening	Screening	-14	-14 to -1	NA
	Baseline	Last assessment prior to first dose of the study treatment. On study day 1, If assessment time is available and before the first infusion or if assessment of height and weight, and questionnaires then it will be considered as baseline.		
Treatment	Day 1	1	1	1

Page 19 of 39

	Week 1	8	2-11	10
	Week 2	15	12-18	7
	Week 3	22	19-25	7
	Week 4	29	26-35	10
	Week 6	43	36-50	14
	Week 8	57	51-64	14
	Week 10	71	65-78	14
	Week 12	85	79-92	14
	Week 12**	85	79-99	21
Optional Treatment	Week 14	99	93-106	14
	Week 16	113	107-127	21
Follow-up	Week 16**	113	100-127	28
	Week 20	141	128-155	28
	Week 24	169	156-183	28

^{*} Study day 1 is the day of the first dose of pegcetacoplan.

Planned visits, as recorded in the eCRF, will be considered first. Only if there is no planned visit recorded in the eCRF (or a planned visit which contains missing data) unscheduled visits will be considered.

If more than 1 record is within the same analysis visit window, the record closest to the target day with non-missing data (the day of the planned visit according to protocol schedule of assessments) will be used in the analysis.

If no planned or unscheduled visit is within the analysis window the data for the visit will remain as missing.

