8.9.5 ANTI-PEGCETACOPLAN AND ANTI-PEG ANTIBODIES

The proportion of patients with positive anti-drug antibodies (ADA) results during the study will be summarized at each visit for the Safety and PK set. Neutralizing antibodies will also be summarized for patients from the Safety set who had positive ADA results.

The proportion of patients with ADA results by category (as outlined below) will be summarized.

- Patients with treatment emergent ADA: any patient negative for ADA at baseline and positive at any post-baseline samples.
- Patients with treatment boosted ADA: any patient positive for ADA at baseline and with a measurable titer at any post baseline sample if the baseline titer was not reportable or with an increase in titer by 4-fold if the baseline titer was reportable.

ADA titers and fold-increases overall and of the maximum titer of each patient will be summarized descriptively with medians, interquartile range (Q1 and Q3) for treatment-emergent, and treatment-boosted ADA, respectively.

ADA will also be listed.

8.9.6 **DEATHS**

The proportion of patients who died will be summarized by cause of death.

Deaths will also be listed.

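### The SAP text summarises the ECG safety endpoint only visit by visit, so it specifies no count of patients who ever had a new or worsened finding; one added row would supply it

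*SAP*

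**What the plan says.** SAP 6.1 lists, among the primary safety endpoints, "Occurrence of clinically significant abnormal electrocardiogram (ECG) findings". Protocol 5.1.2 carries the same endpoint. The one ECG analysis in the SAP is in 8.9.4: "The incidence of clinically significant abnormal ECG findings will be summarized by visit and timepoint". Protocol 8.3.3.2 sets out analyses of adverse events, laboratory values, vital signs and physical examinations, and none of ECGs.

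Two general rules govern the 8.9.4 table:

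- SAP 8.1: "If not specified otherwise, the number of observations with non-missing values will be the denominator for percentage calculation". Section 8.9.4 does not override this.
- SAP 8.3: "Only if there is no planned visit recorded in the eCRF (or a planned visit which contains missing data) unscheduled visits will be considered".

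For comparison, laboratory data get a patient-level summary in SAP 8.9.2: "Shift tables of worst post-baseline assessments (including unscheduled observations) vs. baseline will be presented". Antibody data get one in SAP 8.9.5, where treatment-emergent status means "any patient negative for ADA at baseline and positive at any post-baseline samples".

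A separate route runs through adverse events. Protocol 6.5.5.6 makes the following reportable as an AE: "Any significant ECG finding with an onset time after IMP initiation and that was not present at screening, or worsened during the study". SAP 8.9.1 then tabulates treatment-emergent AEs, counting each patient once at each level of the table.

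**The concern.** The natural reading of an occurrence endpoint is how many of the treated patients had such a finding. A visit table answers a different question: how many of those with an ECG at this visit had an abnormal one. The two agree only in special cases, and the table does not show which case applies.

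Two further features widen the gap. A finding on an unscheduled ECG can be left out. The text also gives no rule for an abnormality that was there before the first dose. At stake is whether the clinical study report can state, by a rule fixed in advance, how many patients met a safety endpoint that the SAP ranks as primary.

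**Working it through.** **Plan's own figure.** The documents give no ECG rate or target. Their only statistical design figure is the 72% probability of at least 8 responders among 12 patients at a true rate of 70%. The exact binomial tail, the sum over k = 8 to 12 of C(12,k) × 0.7^k × 0.3^(12−k), is 0.7237, so that figure reproduces. The ECG point does not depend on it.

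**How many ECG visits a patient has.** Table 1 of the protocol schedules an ECG at every visit. Under its footnote o, a 12-week completer is seen after baseline at Weeks 1, 2, 3, 4, 6, 8, 10, 12, 16, 20 and 24, which is 11 visits. A 16-week completer adds Week 14, and the end-of-treatment visit falls at Week 20, which gives 12.

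**From visit counts to patients.** Let a_j be the number of patients with a finding at visit j. If only planned visits are counted, the number ever affected, N, satisfies

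max(a_j) ≤ N ≤ min(12, sum of a_j).

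Illustrative table: one patient of 12 at each of four visits and none at the others. Then max = 1 and sum = 4, so N can be 1, 2, 3 or 4.

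| Patients ever affected | Proportion | Clopper-Pearson 95% CI |
|---|---|---|
| 1 of 12 | 8.3% | 0.2% to 38.5% |
| 4 of 12 | 33.3% | 9.9% to 65.1% |

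The same visit table supports either row. With one patient of 12 at each of 11 visits, N could be anything from 1 to 11.

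**Unscheduled ECGs.** Under SAP 8.3, an abnormal unscheduled ECG does not enter the table if the planned ECG for that window was recorded with data. A patient whose only finding was on such an ECG adds nothing to any a_j, so even the upper bound above can be too low.

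**Pre-existing abnormalities.** Section 8.9.4 does not say whether an abnormality present before treatment counts. If it does count, the four-visit table could come from one stable pre-existing abnormality, and the number with a new finding could be 0. If it does not, the rule for excluding it is missing.

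**What the AE route adds and leaves out.** New or worsened findings should reach the TEAE tables, but three things separate those tables from an endpoint count:

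1. Protocol 6.5.5.1.1 asks for a diagnosis in place of individual signs and symptoms, so an ECG finding may be recorded under another term.
2. Findings may be spread over several preferred terms or system organ classes. No AE category in SAP 8.9.1 and no Target Medical Event in SAP Appendix IV groups them.
3. TEAE status ends 8 weeks after the last dose. If a 12-week completer's last dose is at about Day 85, the window closes at about Day 85 + 56 = Day 141 (Week 20). The Week 24 ECG on Day 169 is 28 days later.

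**The case against.** The strongest reply is that the patient-level information is already in the plan. Protocol 6.5.5.6 sends new or worsened significant findings to the AE data, whether the ECG was scheduled or not. The TEAE tables count each patient once per level on the Safety set, and SAP 8.1 lists all collected data. With 12 patients, anyone can count from the listing. This largely stands, and it sets the severity. What remains is that no pre-specified row or rule yields the endpoint.

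The table shells are also in a separate document that was not available, so an overall row there cannot be excluded. The denominator is inferred from a default, and SAP 11 requires each table to state its own. Both points are fair. The claim is about the SAP text, which requires no such row.

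The study is a descriptive pilot with no hypothesis tests, and the stopping criteria in Protocol 6.1.5 rest on graded serious events, not on the ECG table. That stands too.

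Two stronger readings are tempting, and the documents do not support either:

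- A reader might infer that deaths and withdrawals make the visit table understate findings. A patient who leaves after a finding stays in the numerator and denominator of the visit where it was seen. Shrinking denominators raise later percentages: one finding is 8.3% of 12, 11.1% of 9 and 16.7% of 6 (9 and 6 are illustrative).
- A reader might infer that a baseline abnormality will be counted at every visit as an on-treatment event. The text is silent on this. It is an ambiguity, not a stated rule.

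**Conclusion.** The concern holds in limited form. The only ECG summary in the SAP text cannot deliver the number of patients with an occurrence, it can omit findings on unscheduled ECGs, and it does not define a new finding. The AE tables and listings recover much of this but contain no count that equals the endpoint.

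No size can be given for this trial, because the documents contain no ECG rate. The range of 1 to 4 of 12 rests on assumed visit counts with all 12 patients assessed at each visit. It shows that the table is ambiguous and does not predict a bias in either direction. The conclusion also assumes that the SAP 8.1 denominator applies and that the unseen shells add nothing. Severity is low: this is a cheap improvement to the reporting of one safety endpoint and does not threaten the study's conclusions.

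**What to change.** In SAP 8.9.4, add a summary on the Safety set: the number and percentage of all dosed patients with at least one clinically significant abnormal ECG after the first dose that was absent before treatment or had worsened. Use scheduled and unscheduled ECGs, and take all dosed patients as the denominator. State which pre-dose ECGs define absence, since Protocol 6.5.5.6 refers to screening while SAP 8.2 generally uses the last pre-dose assessment. State also how worsening is identified when the earlier ECG was already clinically significant, because the three categories in Protocol 6.5.5.6 cannot show it.

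Keep the by-visit table as supportive. A shift from baseline to the worst later category (normal, abnormal but not clinically significant, clinically significant) would match the laboratory display, but it is optional.

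The cost is one row or one short table plus a few lines of SAP text. The ECG classifications and the pre-dose ECGs are already collected. If the shells already contain such a row, only the SAP wording needs to be aligned.
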